12.3.4 Reporting Results

12.3.4.1 Summary of Descriptive Statistics

The change from baseline in GC HCe dose will be summarized by treatment group at Weeks 3, 6, 12, 18 and 24 using descriptive statistics; and the same will also be provided for the percent change from baseline in GC HCe dose.

12.3.4.1.1 Summary of Analysis Results

For [Section 12.3.3.1](#), (a) through (d), the resulting LS mean change from baseline, SE of the LS mean, the difference in LSmean values, tildacerfont – placebo, together with its associated SE and 2-sided p-value will be presented Weeks 3, 6, 12, 18 and 24.

12.4 Primary Efficacy Endpoint Additional Analyses

12.4.1 Per-Protocol and Modified ITT Analysis Sets

The PP and mITT Analysis Sets will provide for additional analyses of the Primary Efficacy Endpoint; and, further, the mITT Analysis Set will provide for additional analyses of the Secondary Efficacy Endpoints. In both instances, only inferences at the Week 24 time point will be presented in these analyses.

12.4.2 Subgroup Analyses

The Primary Efficacy Endpoint Analysis will be repeated using the planned subgroups, by Sex, by Baseline GC dose, by Baseline GC type, by Baseline A4 ULN group.

12.5 Secondary Efficacy Endpoint Analyses

The analysis population for the Secondary Efficacy Endpoint analyses is the ITT analysis set, including all classic CAH subjects who were randomized into the study.

Table 13 Secondary Efficacy Endpoints

Objectives		Endpoints	Analysis
Secondary Efficacy			
To evaluate the effect of tildacerfont in reducing GC use to near-physiologic levels while maintaining androgen control in subjects with CAH	2.1	Proportion of subjects with GC dose \leq 11 mg/m ² /day in HCe and A4 \leq 1.2x baseline or A4 \leq ULN at Week 24	Primary Analysis
To evaluate the effect of tildacerfont in reducing GC use to near-physiologic levels while maintaining androgen control in subjects with CAH	2.2	Proportion of subjects with baseline GC dose \leq 35mg HCe who achieve GC dose \leq 11 mg/m ² /day in HCe and A4 \leq 1.2x baseline or \leq ULN at Week 24	Primary Analysis
To evaluate the effect of tildacerfont in reducing cardiovascular risk in subjects with CAH	2.3	Proportion of subjects with improvement in at least one cardiovascular risk factor at Week 24	Primary Analysis

12.5.1 Statistical Hypotheses for Secondary Efficacy Endpoints

For Secondary Efficacy Endpoint 2.1 the null hypothesis is that the difference between randomized treatment groups in the proportion of subjects achieving GC dose ≤ 11 mg/m²/day in HCe and A4 ≤ 1.2 times baseline or A4 \leq ULN at Week 24 is equal to zero. The alternative hypothesis is that the difference is not equal to zero.

For Secondary Efficacy Endpoint 2.2 the null hypothesis is that in the subset of subjects with a baseline GC dose ≤ 35 mg the difference between randomized treatment groups in the proportion of subjects achieving GC dose ≤ 11 mg/m²/day in HCe and A4 ≤ 1.2 times baseline or A4 \leq ULN at Week 24 is equal to zero. The alternative hypothesis is that the difference is not equal to zero.

Secondary Efficacy Endpoint 2.3 is the proportion of classic CAH subjects who were randomized into the study who improve at least one baseline CV risk factor at 24 weeks from randomization. This proportion is calculated for each treatment group (e.g., placebo, tildacerfont) as the number of subjects at Week 24 who had at least one CV risk factor at baseline (i.e. subjects without any CV risk factors will not be included in the analysis) and no longer meets one or more of the baselines CV risk factors at Week 24, divided by the total number of subjects in the ITT analysis who were randomized to that specific treatment and had at least one CV risk factor at baseline.

12.5.1.1 Statistical Modeling and Testing

The Secondary Efficacy Endpoints are all binary ‘response’ endpoints will be analyzed using logistic regression modelling.

The model for each endpoint will include the responder indicator as the dependent variable; treatment group (0: placebo, 1: tildacerfont); the randomization strata: sex (0: male, 1: female) and baseline GC dose (in HCe, 0: < 40 mg/day, 1: ≥ 40 mg/day); and baseline GC type (0: short-acting, 1: intermediate-acting or combination) as categorical explanatory variables; and, for

Secondary Efficacy Endpoint 2.3, the baseline number of CV risk factors will also be included as a categorical covariate.

An exact score test derived from the logistic regression model, equivalent to an exact CMH test on small sample sizes, will be used to provide the 2-sided p-value to determine whether proportion of responders is different between the tildacerfont treatment group and the placebo treatment group at Week 24. If the logistic model does not converge, a Fisher's exact tests corresponding to the tildacerfont treatment group compared to placebo will be utilized.

12.5.1.2 Multiple Imputation for Missing Response Data

Subjects with missing Secondary Efficacy Endpoint data, data imputed as follows:

Step 1: The missing observations are imputed twenty times to generate complete datasets using SAS® PROC MI with a monotone logistic regression model based on the multiple imputation method. The model shall be:

Responder = Treatment + Sex + Baseline GC Dose group + Baseline GC Type + CAH Type + Response at Week 3, 6, 12 and 18

Step 2: The analysis methods described in [Section 12.3.3](#) will be applied to impute the remaining monotone missing data.

Step 3: The results from the twenty completed datasets are then combined using SAS® PROC MIANALYZE via Rubin's combination rules.

12.5.1.3 Reporting Results

Summary of Descriptive Statistics

For each treatment group, the number and proportions (expressed as percentages) of responders at each scheduled time point will be calculated.

Summary of Analysis Results

The parameter estimates (i.e., least squares [LS] proportions, odds ratios, the 95% CI of odds ratios, nominal p-values from the logistic model will be reported at Week 24.

12.5.1.4 Supportive Analysis CV Risk Secondary Efficacy Endpoint

The responder criterion is systematically varied in order to identify the criteria under which the treatment effect is different. If Secondary Efficacy Endpoint 2.3 is significant, then each successive alternative responder definition will be tested using the methods described in [Section 12.5.1.1](#). For Endpoints 2.3A and 2.3C, subjects who are missing data required to assess CV risk factors at Week 24 will be considered to be non-responders.

Table 14 Alternate Secondary Efficacy Endpoint CV Risk Factor Responder Definitions

Def	Endpoint	Alternative Definition
2.3A	Proportion of subjects with improvement in at least 1 CV risk factor AND no worsening in a CV factor	$\begin{cases} 1 & \text{improvement in } \ge 1 \text{ baseline CV risk factor at Week 24} \\ 0 & \text{no improvement OR worsening} \end{cases}$
2.3B	Proportion of subjects with improvement in at least 2 CV risk factor	$\begin{cases} 1 & \text{no longer meets } \ge 2 \text{ baseline CV risk factor criteria at Week 24} \\ 0 & \text{no improvement} \end{cases}$
2.3C	Proportion of subjects with improvement in at least 2 CV risk factor AND no worsening in a CV factor	$\begin{cases} 1 & \text{improvement in } \ge 2 \text{ baseline CV risk factor at Week 24} \\ 0 & \text{no improvement OR worsening} \end{cases}$

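### Supportive CV responder definitions 2.3B and 2.3C need two baseline factors to improve but keep subjects who had only one, which spoils the reported proportions though not the specified exact test

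*SAP*

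**What the plan says.** SAP 12.5.1 (repeated in Protocol 9.4.3) limits endpoint 2.3 to those "randomized to that specific treatment and had at least one CV risk factor at baseline". The only exclusion it states is that "subjects without any CV risk factors will not be included in the analysis".

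SAP 12.5.1.4 varies the responder criterion to see where the treatment effect differs. If 2.3 is significant, "then each successive alternative responder definition will be tested using the methods described in" 12.5.1.1. In Table 14, 2.3B is "Proportion of subjects with improvement in at least 2 CV risk factor" and requires that the subject no longer meets two or more "baseline CV risk factor criteria at Week 24". 2.3C is "Proportion of subjects with improvement in at least 2 CV risk factor AND no worsening in a CV factor". Table 14 sets no new denominator.

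SAP 12.5.1.1 adds one term to the logistic model for endpoint 2.3: "the baseline number of CV risk factors will also be included as a categorical covariate". The p-value comes from "An exact score test derived from the logistic regression model, equivalent to an exact CMH test on small sample sizes", with Fisher's exact test as fallback if the model does not converge. SAP 12.5.1.3 then calls for responder proportions by arm, LS proportions, odds ratios with 95% CIs, and nominal p-values.

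**The concern.** Endpoint 2.3 drops subjects with no baseline factor, who have nothing to improve. The same logic was not carried to the two-factor definitions. A subject with one baseline factor cannot lose two or improve in two, whatever the treatment does.

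At stake is how the series 2.3, 2.3B, 2.3C is read. A smaller difference for two factors than for one could reflect a weaker effect, or only the presence of subjects who could not qualify. In addition, one level of the specified covariate contains no responders by construction, and logistic regression handles that badly.

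**Working it through.** **The plan's own figure.** The documents give no rate, sample size or power for 2.3, 2.3B or 2.3C. The nearest figure is the study-level one in Protocol 9.2: 45 per group, 30% v 63%, two-sided 0.05, at least 90% power. The normal approximation gives 89.4% (pooled variance) or 91.4% (unpooled). It is reproduced within rounding and is context only.

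**Inputs not in the documents.** The share f with exactly one baseline factor, and the response rates among subjects with two or more. Both are assumed below.

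**1. How likely is the problem?** The chance that at least one of N analysed subjects has exactly one factor is 1 − (1 − f)^N. At f = 5% this is 87.2% for N = 40 and 99.0% for N = 90. At f = 10% or more it is at least 98.5% for N from 40 to 90.

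**2. Count covariate kept.** One simulated example, with treatment and count in the model and 45 per arm (responders/subjects):

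| Baseline count | Placebo | Tildacerfont |
|---|---|---|
| 1 | 0/4 | 0/4 |
| 2 | 1/14 | 6/12 |
| 3 | 4/16 | 5/13 |
| 4 | 3/11 | 5/16 |
| All | 8/45 (17.8%) | 16/45 (35.6%) |

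- The maximum-likelihood coefficient for count 1 does not settle: −6.5, −8.5, −12.5 and −20.5 after 6, 8, 12 and 20 iterations. Its standard error goes from 12.7 to 13,929.
- The treatment log odds ratio is 0.988 (SE 0.513), with or without the eight one-factor subjects.
- The exact p-value stratified by count is 0.0893 both ways. Conditioning on zero responders at count 1 fixes every outcome there, so those subjects carry no information on treatment.
- The LS proportions collapse. Averaging the linear predictor with equal weight over the four levels (an assumption; the SAP gives no weights), placebo at iteration 20 is −1.287 + (−20.488 − 0.224 − 0.214)/4 = −6.52, or 0.1%. Adding 0.988 gives 0.4% for tildacerfont. At iteration 6 the pair was 4.7% v 11.6%. Without the one-factor subjects it is 19.3% v 39.1%, close to the raw 8/41 = 19.5% and 16/41 = 39.0%.
- Fisher's test gives p = 0.094 on everyone and 0.088 on those with two or more factors.

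**3. Count covariate dropped, or Fisher used.** Observed rate = (1 − f) × rate among subjects with two or more factors, so the difference shrinks by the same factor. Assumed 20% v 45% among eligible subjects, 45 per arm before restriction; power is for an unstratified two-proportion test, pooled normal approximation:

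| f | Rates, all | Difference | Power, all | Power, two or more factors |
|---|---|---|---|---|
| 10% | 18.0 v 40.5% | 22.5 | 65.5% | 67.7% |
| 30% | 14.0 v 31.5% | 17.5 | 50.8% | 56.5% |
| 50% | 10.0 v 22.5% | 12.5 | 36.0% | 43.0% |

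The power loss is 2.2, 5.7 and 7.0 points. The crude odds ratio moves from 3.27 to 3.10, 2.82 and 2.61.

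**The case against.** The best defence is that the population is held fixed on purpose. If only the criterion varies, 2.3 and 2.3B answer linked questions in the same people: of those at CV risk, how many lose one factor, and how many lose two? Restricting 2.3B changes criterion and population together. This is a coherent descriptive choice and supports showing the proportion on the wider denominator too. It does not rescue the model as written, and it sits awkwardly with the SAP's own exclusion of subjects with no factor.

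Second, the p-value is exact and Fisher is pre-specified for non-convergence. That stands for the hypothesis test. It does not mend the LS proportions, and the SAP does not say whether quasi-separation counts as non-convergence.

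Third, f may be small. The factors in SAP Table 8 overlap (total and LDL cholesterol, systolic and diastolic pressure, waist and BMI), and a BMI from 27 to below 30 counts only alongside another factor. The sizes above are therefore illustrations.

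A reader might infer that the specified test loses power, or that restriction would gain some. It would not: the exact test stratified by count already sets these subjects aside. Comparing unstratified Fisher on everyone with a stratified exact test on the subset would credit restriction with what stratification achieves.

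**Conclusion.** The structural point is certain from the text: for 2.3B and 2.3C, subjects with exactly one baseline factor are observed non-responders by definition. What follows depends on the model, and the two consequences are alternatives.

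- **Covariate kept, at least one such subject analysed:** quasi-separation confined to one nuisance coefficient. Treatment odds ratio and exact p-value stand; LS proportions cannot be interpreted; the Fisher fallback may be invoked.
- **Covariate dropped, or Fisher used:** proportions and their difference shrink by f, with about 2 to 7 points of power lost at 45 per arm under the assumed rates.

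The raw proportions by arm are reduced in either case. Separation is not unconditional: 12.5.1.1 names the count term for 2.3, and it reaches 2.3B and 2.3C only by cross-reference.

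A related gap: 12.5.1.4 scores missing Week 24 data as non-response for 2.3A and 2.3C but does not name 2.3B. If the imputation of 12.5.1.2 were used there, its model omits the baseline count, so a one-factor subject could be imputed as a responder.

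It would be wrong to read this as a threat to the main results. These analyses are supportive, run only if 2.3 is significant, and lie outside the Hochberg step in SAP 9.6. It is a worthwhile clarification of minor weight.

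**What to change.** In SAP 12.5.1.4 and Table 14:

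- define the analysis population for 2.3B and 2.3C as ITT subjects with at least two baseline CV risk factors;
- start the baseline-count covariate at 2 for these definitions;
- report the number excluded per arm;
- optionally, show the raw 2.3B and 2.3C proportions on the at-least-one-factor denominator, descriptively, so that they can be set beside 2.3 in the same population.

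Eligibility is fixed by baseline data, so the randomised comparison is preserved and no possible responder is lost. Restriction also closes the imputation gap for one-factor subjects. The cost is a few words in the SAP. The downside is that two supportive analyses use a smaller population that differs from that of 2.3. No power gain should be claimed for the specified exact test.

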12.5.2 Subgroup Analyses

Subgroup analyses for Secondary Efficacy Endpoints 2.1, 2.2 and 2.3 will be performed using the planned subgroups, by Sex, by Baseline GC dose, by Baseline GC type, by Baseline A4 ULN group.

12.6 Exploratory Efficacy Endpoint Analyses

The analysis population for Exploratory Efficacy Endpoint analyses is the ITT analysis set, including all classic CAH subjects who were randomized into the study.

The following Exploratory Efficacy Endpoints will be described in this section:

Table 15 Exploratory Efficacy Endpoints

Objectives	Endpoints	Analysis
Exploratory Efficacy		
To evaluate the percentage change in GC use in subjects with CAH	3.1 Percent change from baseline in GC dose at Week 24	Primary Analysis
To evaluate the effect of tildacerfont in reducing the cumulative HCe dose in subjects with CAH	3.2 Change in total cumulative GC dose in HCe at Week 24	Primary Analysis
To evaluate the effect of tildacerfont in improving HOMA-IR in subjects with CAH	3.3 Change from baseline in the HOMA-IR at Week 24	Primary Analysis
To evaluate the effect of tildacerfont in improving HOMA-IR after 52 weeks of tildacerfont treatment in subjects with CAH	3.4 Change from baseline in HOMA-IR at Week 52	Final Analysis
To evaluate the effect of tildacerfont in reducing cardiovascular risk in subjects with CAH	3.5 Proportion of subjects with improvement in at least one cardiovascular risk factor at Week 52	Final Analysis
To evaluate the effect of tildacerfont in reducing GC use to near-physiologic levels while maintaining androgen control in subjects with CAH	3.6 Proportion of subjects with GC dose \leq 11 mg/m ² /day and A4 \leq 1.2x baseline or \leq ULN at Week 52	Final Analysis
To evaluate the effect of tildacerfont in reducing GC use to near-physiologic levels while maintaining androgen control in subjects with CAH	3.7 Proportion of subjects with baseline GC dose \leq 35mg HCe who achieve GC dose \leq 11 mg/m ² /day in HCe and A4 \leq 1.2x baseline or \leq ULN at Week 52	Final Analysis
To evaluate the effect of tildacerfont in improving quality of life in subjects with CAH	3.8 Change from baseline at Week 24 in the SF-36 domains and composite scores	Primary Analysis
To evaluate the effect of tildacerfont in improving quality of life in subjects with CAH	3.9 Change from baseline at Week 52 in the SF-36 domains and composite scores	Final Analysis
To evaluate the effect of tildacerfont on BMI after 24 weeks in subjects with CAH	3.10 Percent change from baseline in BMI at Week 24	Primary Analysis
To evaluate the effect of tildacerfont on BMI after 52 weeks of tildacerfont treatment in subjects with CAH	3.11 Percent change from baseline in BMI at Week 52	Final Analysis
To evaluate the effect of tildacerfont on waist circumference after 24 weeks of tildacerfont treatment in subjects with CAH	3.12 Change from baseline in waist circumference at Week 24	Primary Analysis
To evaluate the effect of tildacerfont on waist circumference after 52 weeks of tildacerfont treatment in subjects with CAH	3.13 Change from baseline in waist circumference at Week 52	Final Analysis

Objectives	Endpoints		Analysis
To evaluate the effect of tildacerfont in improving body composition after 24 weeks of tildacerfont treatment in subjects with CAH	3.14	Change from baseline in percent total fat mass and total percent lean mass at Week 24	Primary Analysis
To evaluate the effect of tildacerfont in improving body composition after 52 weeks of tildacerfont treatment in subjects with CAH	3.15	Change from baseline in percent total fat mass and total percent lean mass at Week 52	Final Analysis
To evaluate the effect of tildacerfont in improving BMD after 52 weeks of tildacerfont treatment in subjects with CAH	3.16	Change from baseline in BMD at Week 24 and Week 52	Primary (Week 24) and Final Analysis
To evaluate the effect of tildacerfont in reducing TART(s) in male CAH subjects with TART(s) at baseline after 24 weeks of tildacerfont treatment in subjects with CAH	3.17	Reduction in TART volume at Week 24 in male subjects who had TART(s) at baseline	Primary Analysis
To evaluate the effect of tildacerfont in reducing TART(s) in male CAH subjects with TART(s) at baseline after 52 weeks of tildacerfont treatment in subjects with CAH	3.18	Reduction in TART volume at Week 52 in male subjects who had TART(s) at baseline	Final Analysis
To evaluate the effect of tildacerfont in reducing GC use while maintaining normal A4 levels at Week 24 in subjects with CAH	3.19	Proportion of subjects with at least a 5 mg/day HCe reduction from baseline (Day 1) in GC dose and $A4 \leq 1.2 \times$ baseline or \leq ULN at week 24	Primary Analysis
To evaluate the effect of tildacerfont in reducing GC use while maintaining normal A4 levels at Week 52 in subjects with CAH	3.20	Proportion of subjects with at least a 5 mg/day HCe reduction from baseline (Day 1) in GC dose and $A4 \leq 1.2 \times$ baseline or \leq ULN at week 52	Final Analysis

12.6.1 Analysis for Change and Percent Change from Baseline at Week 24 Exploratory Efficacy Endpoints 3.1, 3.3, 3.4 and 3.8 to 3.15

A MMRM or ANCOVA model will be used to analyze Exploratory Efficacy Endpoints 3.1, 3.3, 3.4 and 3.8 to 3.15 in the same manner as described in [Section 12.3.3](#); MMRM will be for endpoints with more than one post-baseline assessment, and ANCOVA will be used for endpoints with only one post-baseline assessment at Week 24. The dependent variable will be the absolute or percent change from baseline and the principal treatment effect of interest is at 24 weeks. The LS mean of change from baseline, SE of the LS mean, two-sided 95% CI of the LS mean, LS mean difference of change from baseline between the tildacerfont group and the

placebo (i.e., tildacerfont – placebo), SE of the LS mean difference, and 95% CI of the LS mean difference and its 2-sided p-value will be extracted from the model.

In terms of descriptive statistics, the change from baseline will be reported by treatment group for the reported value and change from baseline value, and percent change from baseline value (if applicable) will be presented by scheduled time point (i.e., Baseline [reported value only] and Week 24).

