To evaluate the effect of tildacerfont in reducing the cumulative HCe dose in subjects with CAH	3.2	Change in total cumulative GC dose in HCe at Week 24	Primary Analysis
To evaluate the effect of tildacerfont in improving HOMA-IR in subjects with CAH	3.3	Change from baseline in the HOMA-IR at Week 24	Primary Analysis
To evaluate the effect of tildacerfont in improving HOMA-IR after 52 weeks of tildacerfont treatment in subjects with CAH	3.4	Change from baseline in HOMA-IR after 52 weeks of tildacerfont treatment	Final Analysis
To evaluate the effect of tildacerfont in reducing cardiovascular risk in subjects with CAH	3.5	Proportion of subjects with improvement in at least one cardiovascular risk factor at Week 52	Final Analysis
To evaluate the effect of tildacerfont in reducing GC use to near-physiologic levels while maintaining androgen control in subjects with CAH	3.6	Proportion of subjects with GC dose $\leq 11 \text{ mg/m}^2/\text{day}$ and A4 $\leq 1.2 \times$ baseline or $\leq \text{ULN}$ at Week 52	Final Analysis
To evaluate the effect of tildacerfont in reducing GC use to near-physiologic levels while maintaining androgen control in subjects with CAH	3.7	Proportion of subjects with baseline GC dose $\leq 35 \text{ mg HCe}$ who achieve GC dose $\leq 11 \text{ mg/m}^2/\text{day}$ in HCe and A4 $\leq 1.2 \times$ baseline or $\leq \text{ULN}$ at Week 52	Final Analysis
To evaluate the effect of tildacerfont in improving quality of life in subjects with CAH	3.8	Change from baseline at Week 24 in the SF-36 domains and composite scores	Primary Analysis
To evaluate the effect of tildacerfont in improving quality of life in subjects with CAH	3.9	Change from baseline at Week 52 in the SF-36 domains and composite scores	Final Analysis
To evaluate the effect of tildacerfont on BMI after 24 weeks in subjects with CAH	3.10	Percent change from baseline in BMI at Week 24	Primary Analysis
To evaluate the effect of tildacerfont on BMI after 52 weeks of tildacerfont treatment in subjects with CAH	3.11	Percent change from baseline in BMI after 52 weeks of tildacerfont treatment	Final Analysis
To evaluate the effect of tildacerfont on waist circumference after 24 weeks of tildacerfont treatment in subjects with CAH	3.12	Change from baseline in waist circumference after 24 weeks of tildacerfont treatment	Primary Analysis

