To evaluate the effect of tildacerfont on waist circumference after 52 weeks of tildacerfont treatment in subjects with CAH	3.13	Change from baseline in waist circumference after 52 weeks of tildacerfont treatment	Final Analysis
To evaluate the effect of tildacerfont in improving body composition after 24 weeks of tildacerfont treatment in subjects with CAH	3.14	Change from baseline in percent total fat mass and total percent lean mass after 24 weeks of tildacerfont treatment	Primary Analysis
To evaluate the effect of tildacerfont in improving body composition after 52 weeks of tildacerfont treatment in subjects with CAH	3.15	Change from baseline in percent total fat mass and total percent lean mass after 52 weeks of tildacerfont treatment	Final Analysis
To evaluate the effect of tildacerfont in improving BMD after 52 weeks of tildacerfont treatment in subjects with CAH	3.16	Change from baseline in BMD after 24 and 52 weeks of tildacerfont treatment	Primary (Week 24) and Final Analysis

Objectives		Endpoints	Analysis
To evaluate the effect of tildacerfont in reducing TART(s) in male CAH subjects with TART(s) at baseline after 24 weeks of tildacerfont treatment in subjects with CAH	3.17	Reduction in TART volume at Week 24 in male subjects who had TART(s) at baseline	Primary Analysis
To evaluate the effect of tildacerfont in reducing TART(s) in male CAH subjects with TART(s) at baseline after 52 weeks of tildacerfont treatment in subjects with CAH	3.18	Reduction in TART volume at Week 52 in male subjects who had TART(s) at baseline	Final Analysis
To evaluate the effect of tildacerfont in reducing GC use while maintaining normal A4 levels at Week 24 in subjects with CAH	3.19	Proportion of subjects with at least a 5 mg/day HCe reduction from baseline (Day 1) in GC dose and A4 $\leq 1.2 \times$ baseline or \leq ULN at week 24	Primary Analysis
To evaluate the effect of tildacerfont in reducing GC use while maintaining normal A4 levels at Week 52 in subjects with CAH	3.20	Proportion of subjects with at least a 5 mg/day HCe reduction from baseline (Day 1) in GC dose and A4 $\leq 1.2 \times$ baseline or \leq ULN at week 52	Final Analysis
4. Exploratory Efficacy (Optional Open-Label Extension Period) (Separate SAP)			
To evaluate the effect of tildacerfont in reducing GC use to near-physiologic levels in subjects with CAH	4.1	Proportion of subjects with GC dose $\leq 11 \text{ mg/m}^2/\text{day}$ in HCe and A4 \leq ULN at EOT	Separate SAP

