12.6.1.2 Subgroup Analyses

Subgroup analyses to Exploratory Efficacy Endpoints 3.1, 3.3, 3.4 and 3.8 to 3.15 will be performed as per [Section 12.5.2](#).

12.6.2 Analysis for Change and Percent Change from Baseline at Week 52 Exploratory Efficacy Endpoints 3.9, 3.11, 3.13, 3.15 and 3.16

An ANCOVA model will be used to analyses Exploratory Endpoints 3.9, 3.11, 3.13, 3.15 and 3.16. The absolute or change or percent change from baseline (placebo-controlled baseline; see section 8.3.9) to 52 weeks will be the dependent variable. The ANCOVA model will include terms for treatment group (0: placebo, 1: tildacerfont); the randomization strata: sex (0: male, 1: female) and baseline GC dose (in HCe, 0: < 40 mg/day, 1: \geq 40 mg/day); and baseline GC type (0: short-acting, 1: intermediate-acting or combination) as categorical explanatory variables. The difference in LSmeans between randomised treatment groups at Week 52 along with the associated CI and 2 sided p-value will be extracted.

Further, a paired t-test will be used to compare the change from tildacerfont-baseline to 52 weeks on treatment with tildacerfont.

In terms of descriptive statistics, for each type of analysis, the change from baseline will be reported by treatment group for the reported value and change from baseline value, and percent change from baseline value (if applicable) will also be presented.

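### SAP 12.6.1 and 12.6.2 put two exploratory endpoints under the wrong time-point model: HOMA-IR at 52 weeks (3.4) and BMD at Week 24 (3.16)

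*SAP*

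**What the plan says.** **Definitions and timing.** SAP Table 5 defines 3.4 as "Change from baseline in HOMA-IR after 52 weeks of tildacerfont treatment" and assigns it to the Final Analysis. Table 15 gives the same endpoint at Week 52, also at the Final Analysis. Table 5 defines 3.16 as "Change from baseline in BMD after 24 and 52 weeks of tildacerfont treatment"; both tables place its Week 24 part at the Primary Analysis and the rest at the Final Analysis. SAP 5.1.3.10 likewise defines the BMD change to both weeks.

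**Week 24 section.** SAP 12.6.1 is headed "Analysis for Change and Percent Change from Baseline at Week 24 Exploratory Efficacy Endpoints 3.1, 3.3, 3.4 and 3.8 to 3.15". It states: "The dependent variable will be the absolute or percent change from baseline and the principal treatment effect of interest is at 24 weeks". Its descriptive statistics cover "Baseline [reported value only] and Week 24".

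**52-week section.** SAP 12.6.2 is headed "Analysis for Change and Percent Change from Baseline at Week 52 Exploratory Efficacy Endpoints 3.9, 3.11, 3.13, 3.15 and 3.16". For its ANCOVA: "The absolute or change or percent change from baseline (placebo-controlled baseline; see section 8.3.9) to 52 weeks will be the dependent variable". It adds that "a paired t-test will be used to compare the change from tildacerfont-baseline to 52 weeks on treatment with tildacerfont".

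**Subsections.** SAP 12.6.1.1 and 12.6.1.2 repeat the first list; 12.6.2.1 and 12.6.2.2 repeat the second.

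**The concern.** Endpoint 3.4 sits only in the section whose effect and summaries are at Week 24. Endpoint 3.16 sits only in the section whose dependent variable is change to 52 weeks. For each, the time point in the definition and the time point of the assigned model disagree.

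Two things are at stake. First, the objective on insulin resistance after 52 weeks of tildacerfont has no assigned model or test at 52 weeks. Second, Week 24 is the only point at which BMD can be compared with a placebo arm, because all subjects move to open-label tildacerfont afterwards. That comparison has no assigned model. If the lists stay as they are, someone must choose the model and the baseline (SAP 8.3.9.1 or 8.3.9.2) outside the plan, possibly after unblinding at the Primary Analysis.

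**Working it through.** No sample size, power or alpha figure is involved. The check matches each exploratory endpoint's time point in Table 15 against the time point of the section that lists it.

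**Results due.** There are 20 endpoints, 3.1 to 3.20. Nineteen have one time point and 3.16 has two, so 19 + 2 = 21 results are due.

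**Results assigned.**

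| SAP section | Time point of the model | Endpoints listed | Number | At the right time point |
|---|---|---|---|---|
| 12.6.1 | Week 24 | 3.1, 3.3, 3.4, 3.8 to 3.15 | 11 | 6 (3.1, 3.3, 3.8, 3.10, 3.12, 3.14) |
| 12.6.2 | 52 weeks | 3.9, 3.11, 3.13, 3.15, 3.16 | 5 | 5 |
| 12.6.3 | each endpoint's own week (responder analyses) | 3.5 to 3.7, 3.17 to 3.20 | 7 | 7 |
| 12.6.4 | Week 24 (cumulative dose) | 3.2 | 1 | 1 |

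Matched: 6 + 5 + 7 + 1 = 19. Unmatched: 21 - 19 = 2, namely 3.4 at 52 weeks and 3.16 at Week 24. The five mismatched listings in 12.6.1 are 3.4, which appears nowhere else, and 3.9, 3.11, 3.13 and 3.15, which 12.6.2 also lists.

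**The data will exist.** SAP 4.3.2.5 schedules HOMA-IR, and SAP 4.3.1.4 schedules DXA, at Day 1 and Weeks 24, 52 and 76.

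**Other text checked for a model.**
- SAP 12.6.5.1 repeats the 3.16 analysis on spine and hip scores. It names no Week 24 model.
- SAP 12.6.5.2 covers fat and lean mass only.
- SAP 12.6.5.5 covers fasting glucose and insulin, not HOMA-IR.
- The protocol synopsis names a general repeated-measures model for HOMA-IR and BMD. Protocol 9.4.4 defers exploratory detail to the SAP, and SAP Section 3 makes the SAP govern where the two differ.

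**Which 52-week analysis answers 3.4.** At Week 52 the tildacerfont arm has had 52 weeks of drug and the placebo arm 52 - 24 = 28. The between-arm ANCOVA in 12.6.2 therefore compares about 52 with about 28 weeks on drug. The paired t-test runs from Day 1 to Week 52 in the tildacerfont arm and from Week 24 to Week 76 (24 + 52) in the placebo arm. HOMA-IR is scheduled at all four visits, so that test is feasible and is the one that matches the objective.

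**After correction.** 12.6.1 would list 7 endpoints, 12.6.2 would list 6, and the other sections 7 + 1. That is 21 of 21, with no duplicates. This counts section labels, not data. Endpoint 3.9 would still lack scheduled Week 52 data, because SAP 4.3.1.6 gives SF-36 only at Day 1, Week 24 and Week 76 in the Treatment Period.

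**The case against.** The strongest reply is that the SAP does commit to both results. SAP 12.1 says the Primary Analysis compares tildacerfont with placebo on the exploratory endpoints in Table 5, which puts Week 24 BMD there. SAP 12.2 does the same for 3.4 at the Final Analysis. SAP 5.1.3.3 and 5.1.3.10 give the right weeks, and protocol 9.1 and 9.4.1 give the Week 52 versus baseline hypothesis and the pooling of arms by time on drug. This stands, and it limits the point: a reader might infer that the two endpoints go unanalysed, and the documents do not support that. But none of this text assigns a model, covariates or a baseline to either result.

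A reader might also infer that 3.4 would simply be reported as a second copy of 3.3. That goes too far. Every definition of 3.4 says 52 weeks, so the reader meets a contradiction between list and definition, not an instruction to duplicate. SAP 12.6.1 uses MMRM where there is more than one post-baseline assessment, so a HOMA-IR model could contain a Week 52 visit. Even so, the section asks only for the 24-week effect, the template in 12.3.3 adds only earlier visits, and the paired t-test still does not reach 3.4.

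Finally, a reader might count 3.9, 3.11, 3.13 and 3.15 as lost or misreported. They are not lost: 12.6.2 lists all four, so their inclusion in the range in 12.6.1 is only redundant.

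**Conclusion.** The point holds as an assignment error: the lists in 12.6.1 and 12.6.2 are wrong as written for two of the 21 results due. Endpoint 3.4 has no assigned 52-week model and no paired t-test. Endpoint 3.16 keeps its Week 52 analysis and lacks only the Week 24 model. The four redundant listings cost nothing beyond clarity.

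Severity is minor. The endpoints are exploratory and outside the testing hierarchy in SAP 9.6, so the primary and secondary results and type I error control do not change. The conclusion assumes that the timings in Tables 5 and 15 are the intended ones and that the section lists would be followed literally.

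**What to change.** Before database lock, amend the SAP as follows.

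- **12.6.1 (Week 24):** list 3.1, 3.3, 3.8, 3.10, 3.12, 3.14 and 3.16 (Week 24 part).
- **12.6.2 (52 weeks):** list 3.4, 3.9, 3.11, 3.13, 3.15 and 3.16 (Week 52 part).
- **Subsections:** carry the same lists into 12.6.1.1, 12.6.1.2, 12.6.2.1 and 12.6.2.2.
- **Endpoint 3.4:** name the paired t-test from tildacerfont-baseline as the analysis that answers the 52-week objective. Label the Week 52 between-arm ANCOVA as a comparison of about 52 with about 28 weeks on drug. Align the Table 5 and Table 15 descriptions of the time point.
- **Endpoint 3.9:** reconcile separately. Moving numbers between lists does not supply a Week 52 SF-36 assessment.

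The cost is SAP wording only. The list corrections need no new data, visits or subjects.
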